3.1 General presentation of summaries and analyses

Statistical analysis and generation of tables, figures, subject data listings and statistical output will be performed using SAS® Version 9.4 or higher. All tables and listings will use Courier New font size 9.

Descriptive statistics will be displayed to provide an overview of the study results. For categorical parameters, the number and percentage of subjects in each category will be presented. The denominator for percentages will be based on the number of subjects appropriate for the purpose of analysis. Unless otherwise noted, all percentages will be displayed to 1 decimal place. No percentage will be displayed for zero counts, and no decimal will be presented when the percentage is 100%. For continuous parameters, descriptive statistics will include number of subjects (n), mean, standard deviation (SD), median, minimum and maximum.

Decimal places for descriptive statistics will always apply the following rules:

- “n” will be an integer,
- Mean, SD, median will use 1 additional decimal place compared to the original data,
- Minimum and maximum will have the same number of decimal places as the original value.

All summaries will be descriptive; no statistical hypothesis testing is planned.

A complete set of listings containing all documented data and all calculated data (eg, change from Baseline) will be generated. Data collected during the Up-Titration Period for DE subjects will be summarized separately.

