8.3 Clinical laboratory evaluations

Clinical laboratory results will be summarized using conventional units. Observed values and change from Baseline values for hematology, biochemistry (including hepatic monitoring of ALT, AST, ALP, total bilirubin, and GGT) and endocrinology parameters will be summarized for Baseline, each scheduled visit in the Evaluation Period, Last Value on Treatment, and the Safety Visit (if available). These summaries will be repeated separately for data collected during the Up-Titration visits for DE subjects.

Presentation of urinalysis results will consider subjects by age group for whom sample collection is feasible due to the constraints on collection for subjects below 4 years of age in the protocol. Following age groups will be presented: ≥ 4 to < 12 years, ≥ 12 years to < 17 years and overall.

In microscopic urinalysis, a small sample of urine is centrifuged to remove the liquid. The sediment is then examined under a microscope. In the urinalysis laboratory test group, other than qualitative responses, a listing of microscopic analysis parameters will be provided; no summaries of microscopic analysis findings are planned.

Response categories are negative, 1+, 2+, and 3+ for the quantitative urinalysis parameters occult blood, leukocytes, glucose, protein, and ketones and negative and positive for nitrates. Outcome values for these parameters are mapped to the levels Negative, 1+, 2+, and 3+ as follows for purposes of summary tables and the determination of PCST:

Table 8-1: Urinalysis categorization

Category	Definition
Negative	“Negative”, “NEGATIVE” or other outcomes that clearly reflect a negative finding
1+	“1+”, “+”, “Trace”, “TRACE” or other outcomes that clearly reflect trace amount
2+	“2+” or “++”
3+	“3+”, “+++” or other outcomes that clearly reflect the data above 3+ (eg, “4+”, “5+” etc.) or more than 4 plus signs (eg, “++++”, “+++++” etc.)

For qualitative urinalysis parameters (occult blood, leukocytes, glucose, protein, ketones, and nitrates), the number and percentage of subjects with each response category will be summarized for Baseline, EV, each scheduled visit during the Evaluation Period for which urinalysis parameters were scheduled to be assessed, Last Value on Treatment, and the Safety Visit. Percentages for each parameter will be relative to the number of subjects with a microscopic urinalysis assessment at each time point. The summary will be repeated for the Up-Titration period for DE subjects.

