8.4 Vital signs, physical findings, and other observations related to safety

8.4.1 Vital signs

Vital signs, including measurements of blood pressure, supine or sitting pulse rate, and body temperature, are assessed after 5 minutes of rest at the ScrV, TV(s), and EV, MEV, FEV, YEV, FV, and at the EDV, Down-Titration Visit (DTV), and the SV in the case of early discontinuation. For LTFU subjects, at the EV, vital sign data will be obtained from the final visit of the core study (if available) and should not be recorded in the eCRF for N01266. If not available, vital signs data will be recorded within N01266 as for DE subjects.

Observed values and change from Baseline value for SBP, DBP, and pulse rate will be summarized for Baseline, EV, each visit during the Evaluation Period for which vital signs or body weight were assessed, EDV, Last Value on Treatment, FV, the Down-Titration Visit (DTV), and the Safety Visit (if available). This summary will be repeated separately for data collected during the Up-Titration visits for DE subjects.

The PCST criteria are based on FDA Division of Neuropharmacological Drug Products guidelines with some UCB-defined additions.

The number and percentage of subjects with any post-Baseline PCST value, any PCST low value, and any PCST high value will be summarized for SBP, DBP, pulse rate, and body weight. This summary will consider all assessments after the first dose of BRV and prior to or on the date of the final dose of BRV (excluding Up-Titration Assessments for DE Subjects). Percentages will be relative to the number of subjects with a post-Baseline assessment. This summary will be repeated for the Up-Titration Period for DE Subjects.

Additionally, the PCST table will be provided stratified by visit for all visits during Evaluation Period. Percentages will be relative to the number of subjects with a value at the corresponding visit.

A subject number table will be provided that identifies subjects with a clinically significant finding after the first dose of BRV for each type of vital sign abnormality.

All vital signs will be provided in subject data listings.

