8.4.2 ECGs

A standard 12-lead ECG is performed at the ScrV, TV(s), and EV, YEV, FV, and at the EDV in the case of early discontinuation. An ECG is performed at the SV only if the ECG results at the EDV are abnormal. At the EV, for LTFU subjects, ECG data will be obtained from the final visit of the core study (if available) and should not be recorded in the eCRF for N01266. If not available, ECG data will be recorded within N01266 as for DE subjects. The Investigator will determine whether the results of the ECG are normal or abnormal and assess the clinical significance of any abnormalities.

The number and percentage of subjects with no abnormality, an abnormal but not clinically significant finding, and a clinically significant finding will be summarized overall and by age group. This summary will consider all assessments after the first dose of BRV in the Evaluation and prior to or on the date of the final dose of BRV. Percentages will be relative to the number of subjects with a post-Baseline assessment in the Evaluation Period. This summary will be repeated for the Up-Titration Period for DE Subjects.

Additionally, this table will be provided stratified by visit for all visits during Evaluation Period. Percentages will be relative to the number of subjects with an ECG assessment at the corresponding visit. Subjects are counted only once at each time point based on the worst observed outcome across all abnormalities reported at that time point.

A subject number table will be provided that identifies subjects with a clinically significant finding after the first dose of BRV for each type of ECG abnormality.

All ECG data will be provided in subject data listings.

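### SAP Section 8.3 bases the qualitative urinalysis percentages on subjects with microscopy, which distorts them at any time point where the two tests have different counts

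*SAP*

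**What the plan says.** Three statements in SAP Section 8.3 bear on this.

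- **What is counted.** The table covers "For qualitative urinalysis parameters (occult blood, leukocytes, glucose, protein, ketones, and nitrates), the number and percentage of subjects with each response category". It is produced for Baseline, the Entry Visit, the scheduled Evaluation Period visits with urinalysis, the last on-treatment value and the Safety Visit, and again for Up-Titration in directly enrolled subjects.
- **What it is divided by.** "Percentages for each parameter will be relative to the number of subjects with a microscopic urinalysis assessment at each time point".
- **What microscopy means here.** Urine is centrifuged, and "The sediment is then examined under a microscope". Of the urinalysis group the section then says: "other than qualitative responses, a listing of microscopic analysis parameters will be provided; no summaries of microscopic analysis findings are planned".

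Elsewhere, Section 3.1 gives the general rule: "The denominator for percentages will be based on the number of subjects appropriate for the purpose of analysis". The by-visit table of PCST vital signs in Section 8.4.1 has "Percentages will be relative to the number of subjects with a value at the corresponding visit", and the by-visit ECG table in Section 8.4.2 has "Percentages will be relative to the number of subjects with an ECG assessment at the corresponding visit".

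**The concern.** A response-category table reads correctly only if the people counted in the categories are the people in the denominator. Here the categories come from the qualitative tests and the denominator from a sediment examination that the section treats as a different kind of result, one for which "no summaries of microscopic analysis findings are planned".

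If the two counts differ at a visit, the categories no longer sum to 100%, and the error can go either way. Fewer subjects with microscopy inflates every percentage. More subjects with microscopy deflates them, which is harder to notice because nothing looks impossible. If the gap between the counts varies from visit to visit, an apparent change over time in, say, protein or occult blood could reflect only how many subjects had microscopy.

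The sentence also leaves the programmer a choice. One can count all qualitative results over the microscopy denominator, or only those of subjects who also had microscopy. These can give different tables.

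**Working it through.** The SAP gives no urinalysis counts and no figure to reproduce, so the check is ratio arithmetic on assumed counts, shown over a range.

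**Notation, for one parameter at one time point**
- Q = subjects with a qualitative result (assumed 100)
- n = subjects in a given category (assumed 90 negative; 60 negative as a second case)
- M = subjects with a microscopic assessment (varied)

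**Formulas**
- Rule as written: category percentage = 100 × n / M; sum over categories = 100 × Q / M
- Matching denominator: category percentage = 100 × n / Q; sum = 100%

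**Results under the rule as written, Q = 100**

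| M | Negative if n = 90 | Negative if n = 60 | Sum of categories |
|---|---|---|---|
| 110 | 90/110 = 81.8% | 60/110 = 54.5% | 100/110 = 90.9% |
| 100 | 90/100 = 90.0% | 60/100 = 60.0% | 100/100 = 100% |
| 90 | 90/90 = 100.0% | 60/90 = 66.7% | 100/90 = 111.1% |
| 60 | 90/60 = 150.0% | 60/60 = 100.0% | 100/60 = 166.7% |
| 40 | 90/40 = 225.0% | 60/40 = 150.0% | 100/40 = 250.0% |

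With the matching denominator, negative is 90/100 = 90.0% or 60/100 = 60.0% in every row, whatever M is.

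**When a single category passes 100%.** This requires n / M > 1, that is M / Q < n / Q. The share with microscopy must be below the share in that category, and the numerator must include subjects without microscopy. The sum of the categories passes 100% as soon as M < Q.

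**If the numerator is restricted to subjects with microscopy.** No category can then exceed 100%. Take Q = 100, n = 90 negative and M = 60, all 60 having a qualitative result. Then 100 − 60 = 40 valid qualitative results are dropped. The negative percentage depends on where the 10 non-negative subjects fall:
- all 10 among the 60: 50/60 = 83.3%
- spread in proportion (6 among the 60): 54/60 = 90.0%
- none among the 60: 60/60 = 100.0%

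The full-data value is 90.0%. Restriction is harmless only if having microscopy is unrelated to the qualitative result.

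**Consistency with the rest of the SAP.** The vital-sign and ECG by-visit tables both divide by subjects who had the measurement being tabulated. The laboratory PCST summary, also in Section 8.3, divides by subjects with an on-treatment assessment. The qualitative urinalysis table is the exception.

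**The case against.** The strongest reply is that this is a slip of terminology. Section 8.3 labels loosely: it calls occult blood, leukocytes, glucose, protein and ketones quantitative in one paragraph and qualitative in another. Appendix 12.2 puts erythrocyte or leukocyte count ranges on the same four-point scale as the graded parameters, so the line between the tests is not perfectly clean. Section 3.1 and the by-visit vital-sign and ECG tables point to the intended denominator, and a programmer might simply use it.

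Much of this is fair, and the sentence may well be a drafting error. It remains a specific rule, and a specific rule normally overrides the general one in Section 3.1. *Microscopic* cannot be read as another name for the tabulated parameters: the section has just defined it as sediment examination and set it apart from the qualitative responses, and Appendix 12.2 grades protein, glucose and ketones by concentration rather than by count.

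A second reply is that the consequence depends on something the SAP does not give, namely how often microscopy is done. That stands in full. A reader might infer that every percentage in the table is wrong, or that values above 100% will appear. The document supports neither. Only time points with unequal counts are affected, and a category above 100% needs the two further conditions shown in the working.

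A third reply is that little hangs on this table. That also stands. The summaries are descriptive, the primary variables are treatment-emergent adverse events and serious adverse events, counts accompany the percentages, and all laboratory data are listed, so a reader could detect and recompute a distortion.

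**Conclusion.** The stated denominator is wrong for this table: it belongs to a different test from the numerator, and nothing elsewhere in the SAP corrects it. That conclusion rests on the wording alone and needs no assumption.

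The numerical size cannot be fixed from the document. On an assumed 100 qualitative results, the category sum is 90.9% with 110 microscopy assessments, 100% with 100, 111.1% with 90 and 166.7% with 60. If both tests are always done together, the effect is nil.

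The damage is confined to the descriptive qualitative urinalysis table and its Up-Titration repeat. It does not reach the adverse event summaries or the urinalysis PCST summary, and it gives no ground for doubting the study's safety conclusions as a whole. This is a small correction, worth making because documenting long-term safety is the primary objective and the present wording can lead to different tables.

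**What to change.** In Section 8.3, replace the denominator sentence so that each percentage for a qualitative urinalysis parameter is based on the subjects with a non-missing result for that same parameter at that time point. Apply the same rule to the Up-Titration repeat. While editing, use one label, qualitative, for these parameters throughout the section.

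The cost is one sentence in the SAP and a matching line in the table specification. No additional data are needed. If both tests turn out always to have been done together, the change alters no figure.

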3.3 Definition of Baseline values

Baseline for all study outcomes will be determined using different methods depending on whether the subject is LTFU or DE.

Unless otherwise specified, Baseline values will be determined as follows:

- DE subjects: the last (most recent) available pre-dose measurement of the corresponding outcome will be used as Baseline
- LTFU subjects:
 - if available, Baseline values from the previous BRV core studies will be used as Baseline
 - otherwise the last (most recent) available measurement assessed between day of final on-treatment measurement in core study and the day before first BRV administration in N01266 will be used as Baseline

For laboratory parameters, vital signs (systolic blood pressure [SBP], diastolic blood pressure [DBP], and pulse rate), body weight, and ECGs, Baseline values will be determined as follows:

- DE subjects: the last (most recent) available pre-dose measurement of the corresponding outcome will be used as Baseline
- LTFU subjects: the last (most recent) available scheduled or UV assessment up to the day of subjects first BRV administration in core study will be used as Baseline (most recent measurement up to first BRV administration in core study, not in N01266 as in the general definition of Baseline values)

Baseline will be determined separately for each individual clinical laboratory parameter for hematology, biochemistry, endocrinology and urinalysis assessments.

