4.2 Handling of dropouts or missing data

The method for handling missing and partial data for medications and AEs is described in Section 3.10.4.1 and Section 3.2.3.1 respectively. Missing AE intensity or relationship will be imputed according to worst case scenario with severe intensity and assumed to be related. For other safety variables, no imputation methods are planned.

Regarding efficacy variables, endpoints using seizure frequency and seizure free days based on DRC data will be calculated over non-missing diary days during each study period or time interval as described in Section 3.10.3.1; days for which seizure diary data were not obtained will not be considered in the calculation of seizure frequency or seizure days. This is applicable to the analysis taking all seizure categories into account as well as to the analysis taking only POS seizures into account. Generally, compliance with the daily seizure diary is expected to be high in a refractory population and, therefore, the impact of missing diary data is expected to be minimal. Because the evaluation of efficacy is not the primary objective of this study, and because this is an uncontrolled study in a variable setting, which allows individualized optimization of dosing of BRV and concomitant AEDs, no summaries assessing the impact of missing seizure diary days are planned.

For subjects who prematurely discontinue during the Up-Titration, Evaluation or Down-Titration Period, the calculation of seizure frequency, seizure free days and seizure freedom will be based on available seizure diary days while the subject was receiving BRV. This effectively imputes the unobserved seizure frequency after discontinuation with the seizure frequency observed prior to discontinuation. The presence of such dropouts may influence the evaluation of the long-term outcomes for subjects who either do not discontinue or do not discontinue early in the study. Therefore, as described below, selected summaries will be produced by exposure duration cohorts to allow an assessment of long-term outcomes without the potentially confounding influence of earlier discontinuations.

Endpoints using seizure data from EEG will only include available data. No imputation method will be conducted.

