The number and percentage of subjects with any post-Baseline PCST value, any PCST low value, and any PCST high value for hematology, biochemistry and urinalysis will be summarized for the Evaluation and Safety Periods separately and for the Evaluation and Safety Period combined by laboratory parameter overall and by age group. PCST criteria for hematology and biochemistry are presented in Appendix Section 12.1 A urinalysis value is considered PCST abnormal if an upward shift of at least 2 degrees from the Baseline occurs under investigational treatment. Percentages will be relative to the number of subjects with an on-treatment assessment.

Observed values and change from Baseline value tables will only present scheduled visits, whereas for PCST tables, values reported at an UV will be summarized under the preceding scheduled visit if the abnormality was not already reported at the preceding scheduled visit. Treatment emergent for this analysis includes any PCST laboratory abnormalities observed during the Evaluation Period.

A subject number table will be provided that identifies subjects with a PCST finding after the first dose of BRV for each type of laboratory abnormality.

All laboratory parameters (planned and unplanned parameters and assessed on scheduled and unscheduled visits) will be provided in subject data listings.

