12.2 PCST Criteria for Urinalysis

Qualitative urine parameters are generally reported by a descriptive score, which differs among laboratories. For data analysis purpose, a four-point scale is used. Five-point, six-point, or seven-point scales will be collapsed into a four-point scale first. A value is considered possibly clinically significant treatment-emergent abnormal if an upward shift of at least 2 degrees from the Baseline occurs under investigational treatment. To collapse the results in a five-point scale into a four-point scale, the lowest 2 positive results will be combined (see example below).

Conversion of results in a five-point scale into a four-point scale

Original Five-point Scale	Four-point Scale
Negative/None	Negative/None
Trace/Rare/Mild/A Few	Trace/1+/Rare/Mild/A Few
1+	
2+/Mod	2+/Mod
3+/Sev	3+/Sev

The original scale and four-point scale for PCST of each urinalysis parameter is described in the table below.

Urinalysis 4-point scales for PCST criteria

PARAMETER	Negative	1+	2+	3+
Protein	Negative	Trace, 30 mg/dL	100 mg/dL	≥ 300 mg/dL, ≥ 1000 mg/dL
Glucose	Negative	100 mg/dL, 250 mg/dL	500 mg/dL	≥ 1000 mg/dL
Ketones	Negative	Trace, 15 mg/dL	40 mg/dL	≥ 80 mg/dL, ≥ 160 mg/dL
Hemoglobin (Occult blood)	Negative	Trace, Small	Moderate	Large
Leukocyte Esterase	Negative	Trace, Small	Moderate	Large
Erythrocytes or Leukocytes	1-5 6-10	11-20	21-25	>25

For parameters which cannot have negative values their lowest two positive values will be in category “Negative”. For parameters which can have negative values their lowest two positive values will be at category 1+.

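### Urinalysis PCST is a shift from Baseline, but its percentage is taken over everyone with an on-treatment sample, so subjects without Baseline urine lower the rate and can never be flagged

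*SAP*

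**What the plan says.** **Numerator.** Section 8.3 states: "A urinalysis value is considered PCST abnormal if an upward shift of at least 2 degrees from the Baseline occurs under investigational treatment". Appendix 12.2 repeats the criterion, calling a value "abnormal if an upward shift of at least 2 degrees from the Baseline occurs under investigational treatment". Neither place gives an absolute cut-off or says what happens when Baseline is missing.

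**Denominator.** The next sentence of Section 8.3 reads: "Percentages will be relative to the number of subjects with an on-treatment assessment". It serves hematology, biochemistry and urinalysis alike.

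**Baseline.** For laboratory parameters in LTFU subjects, Section 3.3 takes the last assessment "up to the day of subjects first BRV administration in core study will be used as Baseline" and adds the clarification "most recent measurement up to first BRV administration in core study, not in N01266 as in the general definition of Baseline values". It also says: "Baseline will be determined separately for each individual clinical laboratory parameter for hematology, biochemistry, endocrinology and urinalysis assessments". Urinalysis Baseline can therefore be missing even when the other laboratory Baselines are present.

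**Missing data.** After dealing with adverse events and medications, Section 4.2 says: "For other safety variables, no imputation methods are planned".

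**Urine collection and age groups.** Section 8.3 limits the urinalysis presentation to subjects from whom a sample can feasibly be obtained, "due to the constraints on collection for subjects below 4 years of age in the protocol". The columns are 4 to under 12 years, 12 to under 17 years, and overall. Section 6.1 takes the age of LTFU subjects at the Entry Visit (EV) of N01266.

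**The concern.** A denominator of subjects with an on-treatment value suits the fixed limits in Appendix 12.1, because one value on treatment decides whether a limit is crossed. A shift criterion needs two values. A subject with an on-treatment sample but no Baseline cannot be classified, yet the rule in effect counts that subject as not abnormal.

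Elsewhere the SAP treats Baseline-dependent summaries differently. The incidence of new seizure types (Section 3.10.3.1) is taken only over subjects known not to have the type at Baseline, and missing or unassessed Baselines are shown separately. The CBCL and BRIEF shift tables (Sections 9.4 and 9.5) leave out core-study cohorts that have no Baseline. Urinalysis PCST has no such protection.

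At stake is a downward bias, of unknown size, in one safety percentage and the absence of some subjects from the table that identifies those with a PCST finding. It would fall mainly on LTFU subjects. Directly enrolled subjects are at least 4 years old and take Baseline from their last pre-dose value.

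**Working it through.** The SAP gives no rate or count on this point, so there is no figure to reproduce. The check is a reading of the rules followed by simple proportions.

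**1. Does the criterion need a Baseline?** On the four-point scale (Negative, 1+, 2+, 3+) the rises of at least 2 degrees are Negative to 2+, Negative to 3+, and 1+ to 3+. Each needs a known starting level. A 3+ on treatment with no Baseline cannot be classified.

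**2. Can Baseline be missing while on-treatment urine exists?** Yes.
- Section 8.3 acknowledges constrained collection below 4 years.
- The general Baseline rule in Section 3.3 lets LTFU subjects fall back on a later measurement when there is no core-study Baseline. The laboratory rule in the same section has no fallback.
- Section 4.2 imputes nothing here.

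**3. Which columns are exposed?** If the age groups use the age defined in Section 6.1, an LTFU child aged 4 or more at the EV is in the 4 to under 12 group, although the core-study Baseline may date from before age 4. That displayed group can therefore be diluted. Children under 4 at entry who give urine later affect the percentage only if the overall column includes them, which Section 8.3 does not say.

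**4. Size.** Let N be the subjects with an on-treatment value, m the share of them without Baseline, and p the PCST rate among those with both values.
- Flagged subjects: p × (1 − m) × N
- Rate under Section 8.3: p × (1 − m) × N / N = p × (1 − m)
- Rate with a Baseline-plus-on-treatment denominator: p × (1 − m) × N / ((1 − m) × N) = p

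Neither p nor m is in the SAP. Over assumed ranges, the rate under Section 8.3 would be:

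| m | p = 2% | p = 5% | p = 10% |
|---|---|---|---|
| 0% | 2.0% | 5.0% | 10.0% |
| 5% | 1.90% | 4.75% | 9.5% |
| 10% | 1.8% | 4.5% | 9.0% |
| 20% | 1.6% | 4.0% | 8.0% |
| 40% | 1.2% | 3.0% | 6.0% |

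Example (assumed): with N = 300, m = 20% and p = 5%, 240 subjects are evaluable and 12 are flagged. Section 8.3 reports 12/300 = 4.0%. The evaluable rate is 12/240 = 5.0%.

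**The case against.** **The SAP may already cover this.** Section 3.1 says percentages use the number of subjects appropriate to the analysis, and the PCST table is described as showing post-Baseline values. The first statement is generic and does not displace the explicit rule in Section 8.3. The second describes timing and does not require that a Baseline value exists.

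**High values are not lost.** This stands. A reader might infer that a child who reaches 3+ on treatment goes uncounted. Section 8.3 also plans a by-visit table of response categories that needs no Baseline, and a listing of all laboratory results from scheduled and unscheduled visits. A 2+ or 3+ is therefore listed and, for the children that table covers, counted at scheduled visits. What is missing is an any-time count for subjects without Baseline.

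**The number affected is unknown.** This also stands. A reader might infer that many young children lack Baseline urine. The SAP speaks of constraints and feasibility, not of how often collection failed. One might also reckon that, with ages spread evenly from 1 month to under 4 years, (48 − 12)/(48 − 1) = 76.6% pass age 4 within 3 years. That is the share passing age 4, not the share without Baseline urine. It also assumes a full 3 years, whereas Section 2.3.3 allows participation to end sooner.

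**Under-4 entrants may not be in the table.** If the overall column only pools the two displayed groups, they cannot dilute it, and dilution comes only from subjects in those groups who lack Baseline urine. A reader might add that the youngest have the least long-term safety data. The SAP does not say so.

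**The table is secondary.** All summaries are descriptive, and laboratory tests are listed in Section 2.2.3 as other variables. This bears on severity, not on whether the rule is right.

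**Conclusion.** The point holds as a minor one. As written, the urinalysis PCST percentage equals the evaluable rate times (1 − m), so it is understated by the relative amount m whenever m is above zero and is never overstated. Subjects without Baseline urine also cannot appear in the PCST subject-number table.

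The conclusion rests on the literal denominator in Section 8.3 and on some subjects having on-treatment urine but no Baseline. The collection limits make that foreseeable, but the SAP does not quantify it. If every such subject has a Baseline, nothing changes. Dilution within the 4 to under 12 group further assumes that the groups use age at the EV. Dilution by children under 4 at entry depends on what the overall column means. The defect is confined to the PCST summaries; the SAP does not support a claim that urinary abnormalities go unrecorded.

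**What to change.** In SAP Section 8.3, for urinalysis PCST only:

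- Set the denominator, parameter by parameter, to subjects with both a Baseline and at least one on-treatment value. Leave the hematology and biochemistry denominator as it is.
- Add a row giving the number of subjects with an on-treatment value but no Baseline, and how many of them had any on-treatment 2+ or 3+.
- State whether the overall column includes children under 4 at entry who gave samples later.

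The cost is a few sentences of SAP text, one table row and slightly smaller denominators. No new data are needed.
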